Treating pregnant women is unique in that it impacts *both* the mother and her developing fetus. CDC has highlighted a new initiative called "**Treating for Two**" and advocated research into medication use during pregnancy to take into account the effectiveness and risk-benefit profiles for both pregnant women and the developing fetus (<http://www.cdc.gov/pregnancy/meds/treatingfortwo/>)⁴². Currently, symptomatic genital herpes infection in pregnancy, usually considered more severe than asymptomatic genital herpes, is mostly treated with anti-herpes medications, such as acyclovir, that are effective in suppressing viral shedding and symptoms²³. Acyclovir is also recommended for treating genital herpes after 36 weeks of gestation to prevent vertical transmission of maternal herpes infection to the newborn^{23,24}. On the other hand, asymptomatic genital herpes before 36 weeks of gestation is often left untreated because of a lack of recognized benefits for fetal outcomes (e.g., reducing PTD and LBW). Thus, many women with mild or asymptomatic genital herpes are left untreated, and, consequently, at increased risk of PTD and LBW^{17,19-22}. Untreated genital herpes infection was associated with more than twice the risk of PTD and more than 40% of increased risk of LBW, compared to controls as described above. More importantly, if treated with acyclovir, women with genital herpes had a more than 50% reduced risk of PTD (OR=**0.49**, 95%CI=0.36-0.68), and 40% reduced risk of LBW (OR=**0.60**, 95%CI=0.37-0.98) than women who were not treated (Tables 2). Our preliminary results showed that the currently recommended treatment of herpes infection with acyclovir, if expanded to treat pregnant women with genital herpes before the 3rd trimester, could largely mitigate the risk of PTD and LBW associated with genital herpes infection. This treatment effectiveness was also consistent across subtypes of PTDs.

A lack of consistency in treating genital herpes infection in pregnant women is largely due to the knowledge gap regarding (1) increased risk of PTD and LBW associated with untreated

genital herpes infection in pregnant women, and (2) evidence of treatment effectiveness in reducing PTD and LBW, in addition to preventing mother-newborn vertical transmission of herpes infection^{17,19-21,35}.

A.4. Existing knowledge gaps

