database, we will identify those who are treated with anti-herpes medications (e.g., acyclovir). Thus, four comparators in Stage I samples of all mother-birth dyads (N=90,000) will be established based on the information on genital herpes infection and its treatment and timing of the treatment (see **Figure 1**): pregnant women with genital herpes who are treated *before* the 3rd trimester (Cohort A), pregnant women with genital herpes who are treated *after* the 3rd trimester (Cohort B), women with genital herpes, but untreated (Cohort C), and women with neither genital herpes nor receiving anti-herpes medications (Cohort D). We will also randomly select 300 pregnant women from each of the four cohorts for Stage II sampling to conduct telephone interviews to ascertain more detailed medical history of genital herpes infections (for Cohorts A, B & C), compliance with prescribed medication treatment during pregnancy (Cohorts A & B), and potential confounders including risk factors for PTD and LBW (for all Cohorts). The questions in the Specific Aims will be addressed using the Cox proportional hazards regression model in analyses of PTD analysis, accommodating delayed entry into the cohort and time-dependent covariates⁴⁵⁻⁴⁷, and logistic regression in analyses of LBW. The analysis will incorporate the large sample size from Stage I (all 90,000 births) and rich information on additional confounders and compliance from Stage II interviews. The schematic description of the two-stage study design and cohorts is presented in Figure 1.

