3.3 Study Population

3.3.1 Inclusion Criteria

- 1) Females \geq age 18
- 2) Kaiser members
- 3) Pregnant beyond 20 weeks of gestation during the recruitment period
- 4) Cohort A: pregnant women with genital herpes who are treated before the 3rd trimester

Cohort B: pregnant women with genital herpes who are treated after the 3rd trimester

Cohort C: pregnant women with genital herpes, but untreated

Cohort D: pregnant women with neither genital herpes nor receiving anti-herpes medications

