3.3.3 Populations

Stage I population

All KPNC women aged 18 years (the minimum age required by our KPNC IRB) or older who are pregnant beyond 20 weeks of gestation during the recruitment period will be included to form the Stage I population, estimated at 90,000. These women will be assigned to one of the four cohorts based on diagnosis and treatment of genital herpes infection. Identification of genital herpes will be based on information from multiple databases captured by KPNC EMR including clinical diagnosis, laboratory testing and viral culture, prenatal screening inventory, and medical history. Treatment will be determined through prescription and dispensing of anti-herpes medications from the pharmacy data. Based on the combination of infection and treatment as well as the specific aims, we expect to establish four cohort groups. information currently available information, we expect a total of 2,100 women with genital herpes receiving treatment before the 3rd trimester (Cohort A), 2,100 women with genital herpes receiving treatment after the 3rd trimester (Cohort B), 6,600 women with untreated genital herpes (Cohort C), and 79,200 controls with neither genital herpes nor treatment (Cohort D), as shown in Figure 1. A small adjustment may need to be made at the end of pregnancy, if the status of the infection and/or treatment has changed since the initial assignment to each comparator (e.g., from untreated to treated). Through the KPNC EMR, we will have information on genital herpes infection and treatment during pregnancy (the exposure variables), and PTD and LBW (the outcome variables) (Table 4) as well as many potential confounders (Table 5) for all 90,000 pregnant women. This large Stage I population will provide a large powerful study population to examine comparative effectiveness of genital herpes treatment in reducing adverse pregnancy outcomes, addressing the questions listed in the specific aims.

Stage II samples

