A sample of 300 pregnant women from each of the four cohorts described above (Figure 1) will be randomly selected to form Stage II samples. The random selection will be spread evenly throughout the study period so that all of the estimated 90,000 participants in Stage I will have an equal chance of being selected. They will be selected after their inclusion in Stage I with known status of infection and treatment, mostly before the 3rd trimester to avoid interviewing after delivery to reduce participation and recall biases. Infection status will largely be known in the 1st or early 2nd trimester after the universal STD screening. Any change in exposure status (infection and treatment) after initial assignment will be rectified and finalized during analyses, as we have done in other similar studies with two-stage design (with different exposures in pregnancy).

Participants in Stage II samples will be interviewed to obtain more detailed information on characteristics of genital herpes infection, including history of the infection (e.g., age at initial infection, history of recurrence and treatment), whether it is a primary or latent infection, symptomatic or asymptomatic, etc. While our EMR has information on some of these characteristics of the infection, especially those ascertained through the prenatal screening tool, this Stage II interview will provide us additional characteristics of the infection to allow for assessment and thus to examine whether the treatment effectiveness varies depending on those infection characteristics (e.g., more effective for recent vs. past infection, and age at onset of initial infection, etc.).

The Stage II samples will also allow for direct ascertainment of compliance with prescribed medications. Studies based on pharmacy data alone usually have to make an assumption of 100% compliance with dispensed medications. In this study, we can directly examine the compliance and assess its potential impact on treatment effectiveness. This will be an important strength for this pharmacoepidemiologic study.

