Point and interval estimates of the hazard ratio for PTD associated with untreated genital herpes, vs. no infection, will be calculated as described above, using Cox regression (Cohort C vs. D). The approach to inclusion of potential confounders, modeling continuous covariates, and model diagnostics is as described above.

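### Aim 5 contrasts cohort labels that later treatment can change, so read literally the estimate for untreated infection (C vs. D) is biased upward; the person-time rule needs stating

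*Combined protocol and SAP*

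**What the plan says.** - **Contrast.** Section 4.2, Aim 5: the PTD hazard ratio is to be obtained by the methods already set out for the preceding aims, "using Cox regression (Cohort C vs. D".
- **Label.** Section 3.3.1: "Cohort C: pregnant women with genital herpes, but untreated". No gestational age is attached to being untreated.
- **Reclassification.** Section 3.3.3, Stage I population: "A small adjustment may need to be made at the end of pregnancy, if the status of the infection and/or treatment has changed", with untreated to treated as the example. Under Stage II samples: "Any change in exposure status (infection and treatment) after initial assignment will be rectified and finalized during analyses".
- **Timing of late treatment.** Section A.3: "Acyclovir is also recommended for treating genital herpes after 36 weeks of gestation". No other information is given on when Cohort B starts treatment within the 3rd trimester.
- **Time dependence.** Section 3.1 says the PTD questions in the Specific Aims will use Cox regression "accommodating delayed entry into the cohort and time-dependent covariates". Section 4.2 makes treatment time-varying under Aim 2, with three levels: none, first treated before the 3rd trimester, and treated during it. None of these levels is an uninfected group.
- **LBW.** Section 4.2 uses logistic regression for LBW in all five aims.

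**The concern.** If the final label is used as a fixed exposure, membership of C depends on what happens later. A woman who delivers at 33 weeks has lost the chance of treatment after 36 weeks and remains in C. An otherwise identical woman still pregnant at 36 weeks may be treated. She then moves to B and takes her untreated weeks out of the contrast. C keeps the early deliveries and loses some of the pregnancies that lasted.

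Propensity strata (Section 4.3) would not cure this. They balance measured covariates, not the opportunity to stay pregnant long enough to be treated.

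Aim 5 is the plan's evidence on the harm of leaving infection untreated, and Section 2 intends the results to inform policy recommendations. With all 90,000 women contributing, a modest bias can look highly significant.

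**Working it through.** **1. The plan's own figure.** Table 6 gives detectable hazard ratios for C vs. D of 1.51 (8% PTD) and 1.40 (11%). Section 4.5 uses an effective 1,200 per cohort, two-sided alpha .05 and power .80. Reading the rate as the overall rate:

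- Events: 2,400 × 0.08 = 192; 2,400 × 0.11 = 264.
- HR = exp[(1.960 + 0.842)/√(events × 0.25)] = 1.498 and 1.412.

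These agree with Table 6 (power 0.815 and 0.780 at the stated ratios). The LBW odds ratios of 1.54 and 1.47 also reproduce (power 0.81 and 0.80).

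**2. Bias under the null, by arithmetic.** Inputs from Section 3.3.3: B = 2,100, C = 6,600, D = 79,200. The PTD rate is r = 8% (Section 4.5). Assume neither infection nor treatment has any effect. Let f be the share of PTDs that occur before late treatment would begin; the documents do not give f.

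- PTDs among the women in B and C together: 8,700r = 696.
- PTDs in B, whose members must still be pregnant when treated: 2,100 × r(1−f)/(1−rf).
- Risk in C: (696 − PTDs in B)/6,600.
- HR = ln(1 − risk in C)/ln(1 − r).

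| f | PTDs in B | Risk in C | HR |
|---|---|---|---|
| 25% | 128.6 | 8.60% | 1.08 |
| 50% | 87.5 | 9.22% | 1.16 |
| 75% | 44.7 | 9.87% | 1.25 |
| 100% | 0 | 10.55% | 1.34 |

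The last row is the bound: no woman in B delivers preterm. For rates of 8% to 12% the bound is HR 1.34 to 1.35.

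**3. Chance of a false positive at f = 50%.** ln(1.16) ≈ 0.148.

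- Full Stage I: SE = √(1/608.5 + 1/6,336) = 0.0424, z = 3.5, rejection about 94%.
- 1,200 per cohort: SE = √(1/110.6 + 1/96) = 0.139, z = 1.06, rejection about 19%.

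Across f = 25%, 50%, 75% and 100%, the figures are about 40%, 94%, 100% and 100% at full size, and 8%, 19%, 36% and 57% at the planning size.

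**4. Simulation under the null.** Each setting had 40 replicates with 10,800 infected women, 79,200 controls and entry at 20 weeks. Assumed, not in the documents: PTDs split 6/12/12/30/40% over weeks 20–28, 28–32, 32–34, 34–36 and 36–37, and the treatment-start windows below.

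| Treatment start in B | Fixed label, 8% | Fixed label, 11% | Untreated time to first treatment |
|---|---|---|---|
| 28–32 wk | 1.04 | 1.03 | 0.99–1.00 |
| 28–40 wk | 1.15 | 1.16 | 1.00–1.01 |
| 32–38 wk | 1.16 | 1.17 | 0.99 |
| 36–38 wk | 1.31 | 1.32 | 1.00–1.01 |

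Counting untreated time up to first treatment removes the bias in every setting.

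**5. A time-varying treatment term alone does not help.** If only women finally labelled C or D are analysed, treatment is zero at every week for all of them, so the term cannot change the estimate. What matters is whether the pre-treatment weeks of B are put back.

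**6. LBW.** Logistic regression has no risk sets, so the final label is the exposure. If B had no LBW, the same arithmetic bounds the spurious odds ratio at about 1.36 (8% rate) and 1.37 (10%). The real bias would be smaller, because LBW also occurs at term.

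**The case against.** The strongest reply is that the plan already intends time-varying classification for PTD. Section 3.1 covers all the Specific Aims questions, Aim 2 wants exposure classified properly within each risk set, and Aim 5 refers back to the methods above it. The Section 3.3.3 wording on rectifying status is compatible with splitting person-time, and nowhere does the plan say that pre-treatment weeks are discarded. On that reading the null hazard ratio is about 1.0.

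This stands as a possible intention, so a reader who infers that C is certainly enriched for preterm births goes further than the documents allow. It does not settle the matter. Aim 5 still names C vs. D and does not restore Cohort B's earlier weeks. The Aim 2 levels offer no uninfected reference, and what Aim 5 expressly carries over is confounders, continuous covariates and diagnostics. For LBW the reply is not available.

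The reply on size also stands in part. Cohort B covers the whole 3rd trimester, and if most starts fall soon after 28 weeks the bias is only 1.03 to 1.04. The high false-positive rates assume full Stage I precision, whereas the plan bases power on 1,200 per cohort.

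**Conclusion.** The point holds as a defect in how Aim 5 is written. For PTD the exposure rule is unresolved, and its literal reading is biased upward. For LBW the final label is the only exposure the method allows.

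With no true effect, the spurious PTD hazard ratio is about 1.03 to 1.32, with a bound of about 1.35. The cohort sizes and rates are the plan's. The treatment-start distribution and the gestational split of PTD are assumptions, and the 36-week statement in Section A.3 is the only timing given.

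Three stronger inferences are not supported:

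- **That the bias accounts for the preliminary odds ratio of 2.23.** The bound is far below it, and also below the detectable ratios in Table 6.
- **That 2,100/8,700 = 24% is the true size of what the plan calls a small adjustment.** Section 3.3.3 fixes no date of initial assignment, so it is not known how many women in B were ever assigned to C.
- **That Aim 1 is biased in the same way.** This follows only if fixed labels are used there. Aim 2 extends the Aim 1 model with time-varying treatment, and no size has been worked out for Aim 1.

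**What to change.** **PTD, Aim 5.** Replace the C vs. D contrast with untreated infected person-time vs. Cohort D, on the gestational-age scale. Each infected woman counts as untreated from cohort entry to her first anti-herpes dispensing. This includes the pre-treatment weeks of women later in B, and of women in A first treated after 20 weeks. At first dispensing she is censored or moves to a treated state. If she is censored, adjust for measured predictors of treatment, because censoring may be informative: Section A.3 says symptomatic infection is mostly treated.

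**LBW, Aim 5.** Classify infected women by treatment status at a fixed gestational landmark among those still pregnant, and compare them with Cohort D women still pregnant at that landmark.

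**Both outcomes.** Keep the end-of-pregnancy C vs. D contrast as a sensitivity analysis only. If fixed labels were intended in Aim 1, use the same time-varying classification there.

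**Cost.** A paragraph of plan wording and minor programming; Section 3.3.3 already draws treatment from pharmacy dispensing data. The landmark analysis excludes deliveries before the landmark, which should be stated when it is reported.

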4.4 Instrumental Variable Analysis

We will also use instrumental variable analysis (IVA) methods to assess the sensitivity of our results to unmeasured confounders. IVA is an alternative method for reducing selection bias that addresses both the effects of unobservable characteristics and the issue of dual causality between the choice of a treatment and the health outcome⁵²⁻⁵⁴. IVA methodology uses an indirect attribute that is closely associated with the type of treatment a patient receives, recreating randomized treatment assignment from a trial. This type of analysis requires identifying at least one factor that significantly affects treatment choice but is unrelated to the health outcome. IVA can be used to measure treatment effects independent of selection bias, which helps inform broad policy decisions, but it is limited in guiding clinical decisions for specific population subgroups⁵⁵. We will initially consider physician specific prescribing preference, as measured in the KPNC pharmacy database, as the instrument⁵⁶. It is necessary to consider how the characteristics of patients vary with respect to the instrument used when interpreting results of an IVA⁵². Our access to a rich amount of data will permit a thorough evaluation of the validity of our candidate instruments. If our selected instrument appears to be valid, and we find that IVA yields different results compared with PS analysis, we will have confirmed the likelihood of unmeasured confounding in our PS analysis. Given the extensive control for confounding using our clinical data, and the large sample sizes, we anticipate PS analysis and IVA to yield similar results. However, if IVA yields results that vary from PS results, and our instruments are reasonably valid, it suggests the presence of unmeasured confounders in our treatment comparisons in the PS and traditional analyses. Thus, it

will inform in the interpretation of findings with respect to possible impact of unmeasured confounders.

While we expect no or very little missing data on treatment exposure, pregnancy outcomes and potential confounders, we will assess all variables under study for missingness. If necessary, we will utilize multiple imputation techniques using multivariate sequential regression⁵⁷.

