4.5 Sample Size and Statistical Power

Given the lack of established methods for power calculations for the SMLE in our two-stage sampling scheme, we provided minimum detectable effect estimates using the results from a simulation study that we have conducted. The study provides information on the expected efficiency gains of the two-stage SMLE, relative to a standard regression analysis of the Stage II sub-sample only (with complete data on all confounders in addition to exposure and PTD/LBW status). For the purposes of our simulation study, we made a few simplifying assumptions. We assumed three exposure categories: no infection, infection with treatment, infection without treatment, with population prevalence set at 87%, 8% and 5% (similar to preliminary data), and outcome relative risks of 1.0 (ref), 1.5 and 2.0, respectively. We assumed one binary confounder measured in the Stage II sub-sample with varying prevalence across exposure categories and strength of association with outcome. The pregnancy outcome incidence was assumed at 8% (among those unexposed to infection). The Stage I sample size was 90,000, with random selection of 300 in each of the two infection/treatment categories. Relative efficiencies [i.e. $\text{Var}(\text{Stage II MLE}) / \text{Var}(\text{SMLE})$] ranged from 4 to 82 across the scenarios, demonstrating substantial gains by utilizing exposure and outcome information in the full sample of 90,000.

As an approximation to the impact of utilizing exposure and outcome information on 90,000 Stage I women in combination with the Stage II sub-sample of 1200 women, we took an “effective sample size” approach, and assumed the worst case among the simulation scenarios considered, where the relative efficiency of the SMLE was approximately 4.0. Thus, rather than basing power calculations on the Stage II sample size of 600 (300 in each group, for a two-group contrast), we based them on 2400 (i.e. $4.0 * 300$; 1,200 in each cohort category). We acknowledge that estimated gains in efficiency are based on results from a simulation study and may vary in actual analysis.

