Power calculations are based on the likelihood ratio test in the context of a Cox proportional hazards regression analysis for PTD, and a logistic regression analysis for LBW, as presented by Self⁵⁸ and as implemented in the software package EGRET⁵⁹. Given previous experience⁶⁰⁻⁶³, we expect negligible loss to follow-up (< 0.20%), a rate of PTD ranging from 8% - 12%⁶⁴, and LBW ranging from 8% to 10%⁶⁵. Each primary contrast of interest in analyses addressing **Aims 1, 2 and 5** can be characterized as a comparison of two groups of women with respect to risk of PTD and LBW. Minimum (maximum, for protective effects) detectable associations are of modest to moderate strength (Table 6). The proposed study will have more than sufficient power to detect the associations observed in our preliminary studies. Relevant to **Aim 3**, we present the maximum (protective effects assumed) detectable pattern of hazard ratios (HR) across cumulative treatment duration categories (no treatment, 1 – 10 days (45% among treated), > 10 days (55% among treated)). For the purpose of detectable effect calculations, we assume a graded, linear trend in (log) hazard/odds ratios across duration categories, a two-sided test for trend and a significance level of .05. We have sufficient power (.80) to detect a pattern of PTD HRs of 1.0 (ref), .82, and .67 associated with no treatment, 1-10 days and >10 days, respectively, assuming the worst case

scenario of expected 8% PTD rate. Similarly, we have sufficient power (.80) to detect a pattern of

Table 6. Minimum (maximum for protective scenarios) detectable hazard ratios (HR) for preterm delivery and detectable odds ratios (OR) for low birthweight in pair-wise comparisons of genital herpes exposure/treatment categories; two-sided test, significance level (α) = .05, power (1- β) =.80.

Contrast	Preterm Delivery (HR)		Low Birthweight (OR)	
	Rate = 8%	Rate = 11%	Rate = 8%	Rate = 10%
Treated infection vs. untreated infection (Aim 1; A+ B vs. C)	.71	.75	.70	.72
Treated < 3 rd trimester vs. 3 rd trimester (Aim 2, A vs. B)	.66	.71	.65	.68
Untreated infection vs. no infection (Aim 5, C vs. D)	1.51	1.40	1.54	1.47

odds ratios ORs of 1.0 (ref), .81, and .66 associated with no treatment, 1-10 days and >10 days, respectively, assuming the worst case scenario of expected 8% LBW rate.

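### Section 4.4 reads a gap between the instrumental-variable and propensity-score results as evidence of unmeasured confounding, without allowing for the gap's sampling error or the instrument's different target population

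*Combined protocol and SAP*

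**What the plan says.** Section 4.4 adds an IV analysis to the PS analysis of section 4.3, with each physician's prescribing preference as the first candidate instrument. On condition that the instrument appears valid, a differing IV result means "we will have confirmed the likelihood of unmeasured confounding in our PS analysis". Later in the same paragraph the wording is softer: "if IVA yields results that vary from PS results, and our instruments are reasonably valid, it suggests the presence of unmeasured confounders". The section closes by saying that the comparison will inform interpretation.

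The section calls for looking at how patient characteristics vary with the instrument, and it promises an evaluation of instrument validity. It expects the two methods to agree, partly because the samples are large. It does not define when two results differ. It gives no IV estimator, effect scale, measure of first-stage strength, or interval for the gap.

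Under section 4.3 the PS analysis is a Cox model (preterm delivery, PTD) or a conditional logistic model (low birthweight), stratified by deciles of the score.

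**The concern.** The only gate on the inference is instrument validity. Two other things can separate the estimates when there is no unmeasured confounding:

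- **Sampling error.** The variance of an IV estimate is roughly the PS variance divided by the share of treatment variance that the instrument explains, so a modest instrument gives a wide estimate.
- **Target population and scale.** A preference-based IV describes women whose treatment depends on which physician they see. The PS analysis gives a stratified hazard or odds ratio over all infected women. If the effect varies between women, both can be right and still differ.

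The study is not randomised and is meant to inform treatment guidelines. Followed as written, the rule could cast doubt on a sound PS estimate. When power is low, a reader could also take apparent agreement as more reassurance than it gives.

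**Working it through.** **The plan's nearest figure.** The documents state no precision for the IV analysis. The closest figure is in Table 6 (section 4.5), row "Treated infection vs. untreated infection (Aim 1; A+ B vs. C": a detectable PTD hazard ratio of .71 at an 8% rate, with "two-sided test, significance level (α) = .05, power (1- β) =.80". Taking "1,200 in each cohort category" gives 2,400 treated against 1,200 untreated, and 3,600 × 0.08 = 288 events. The Schoenfeld formula gives exp(−(1.960 + 0.842)/√(288 × 2/3 × 1/3)) = 0.705, and power 0.78 at HR .71. The table is reproduced closely, but it says nothing about the IV estimate.

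**Inputs.**
- Section 3.3.3: "2,100 women with genital herpes receiving treatment before the 3rd trimester (Cohort A"), and "2,100 women with genital herpes receiving treatment after the 3rd trimester (Cohort B), 6,600 women with untreated genital herpes (Cohort C"). So 4,200 are treated and 6,600 untreated, N = 10,800, and the treated share is 4,200/10,800 = 0.389.
- PTD rate: 10%, inside the 8% to 12% of section 4.5.
- Assumption: R², the share of treatment variance explained by the instrument. With a 50/50 split of physicians into high and low preference, R² = 0.25d²/(0.389 × 0.611), where d is the difference in treated proportion between the two halves. R² of 2%, 5%, 10% and 26.3% correspond to d of about 0.14, 0.22, 0.31 and 0.50.

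**Formulas (risk-difference scale).**
- SE(PS) = √(0.10 × 0.90/(10,800 × 0.389 × 0.611)) = 0.0059, or 0.59 points.
- SE(IV) = SE(PS)/√R².
- With no unmeasured confounding and a homogeneous effect, SD(IV − PS) = √(SE(IV)² − SE(PS)²), the Hausman form.
- Chance of a gap over 2 points = 2 × Φ(−2/SD).
- Power to detect a 3-point bias (two-sided 5%) = Φ(3/SD − 1.96) + Φ(−3/SD − 1.96).

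| R² (assumed) | SE(IV), points | SD of gap, points | Chance of gap > 2 points | Power for 3-point bias |
|---|---|---|---|---|
| 2% | 4.19 | 4.15 | 63% | 11% |
| 5% | 2.65 | 2.58 | 44% | 21% |
| 10% | 1.87 | 1.78 | 26% | 39% |
| 26.3% | 1.15 | 0.99 | 4% | 86% |

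Two points is a fifth of the 10% baseline risk. With PTD at 8% the chances of such a gap are 59%, 39%, 21% and 3%. At 12% they are 66%, 47%, 30% and 6%.

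**Same check against the treatment effect.** Take an untreated PTD rate of 11%.
- For HR .71, the treated risk is 1 − 0.89^0.71 = 7.9%, a difference of −3.1 points. At d = 0.10, 0.20, 0.30 and 0.50, the estimates differ by more than half the true effect 79%, 59%, 40% and 12% of the time by chance.
- For a hazard ratio of 0.49 (the preliminary odds ratio in section A.3, used here as a hazard ratio), the difference is −5.4 points and the chances are 62%, 31%, 12% and 0.4%.

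**Two side results.**
- The first-stage F is (R²/(1 − R²)) × (N − 2). At R² = 2% it is (0.02/0.98) × 10,798 = 220. An instrument can look strong while the estimate is too wide to compare.
- The appeal to large samples does not carry over to the IV. The relevant N is 10,800, not 90,000. N × R² is 216 at 2% and 1,080 at 10%.

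**Simplifications.** SE(PS) is unadjusted, treatment is taken as ever versus never, and clustering by physician is ignored. Clustering would widen the IV estimate.

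**The case against.** The fairest defence is that section 4.4 is more careful than one sentence suggests. Four stronger readings are tempting, and the documents do not support them.

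- **That any difference counts as proof.** The inference is conditional on an apparently valid instrument, stated twice, and the second statement only says that a difference is suggestive.
- **That the IV estimate is necessarily too imprecise.** The documents give no first-stage strength. At R² near 26% a chance gap over 2 points is uncommon (4%) and power for a 3-point bias is good (86%).
- **That this is the plan's only safeguard against confounding.** The Stage II interviews collect confounders absent from the medical record and compare infection characteristics between treated and untreated women (section 3.3.3). The IV analysis is the only check aimed at factors measured in neither stage.
- **That a discrepancy changes the headline, or that agreement is declared to rule out confounding.** Under section 4.3 a conventional-versus-PS difference changes which result is reported as main. Section 4.4 attaches no such switch, and it anticipates agreement without saying what agreement would prove.

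The defence can also point out that covariate patterns across the instrument are already to be examined. All of this limits the point. None of it defines a difference, supplies the uncertainty of the gap, or brings the target population into the inference.

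**Conclusion.** The concern holds in a limited form. Even with a valid instrument, the rule in section 4.4 can attribute to unmeasured confounding a gap that comes from chance or from a different target population. How often depends on instrument strength, which is assumed here. Between R² of 2% and 10% a gap over 2 points arises by chance in 63% to 26% of studies, and a 3-point bias is missed more often than it is found. At about 26% the comparison works reasonably well. Since the plan cannot know in advance where in this range it will fall, the inference should rest on the interval for the gap. The consequence is confined to how the main result is interpreted. The point merits a change to the analysis plan, but it does not call the primary analysis into question.

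**What to change.** Replace the inference rule in section 4.4 with the following:

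1. Estimate the IV and PS effects in the same women and on one stated scale. Define treatment so that women first treated in the 3rd trimester are not credited with earlier time, in keeping with the time-varying treatment of section 4.2 (Aim 2).
2. Report first-stage strength and covariate balance across levels of the instrument.
3. Give a 95% confidence interval for the IV-minus-PS difference from a bootstrap that resamples physicians.
4. Read a difference as consistent with unmeasured confounding only if that interval excludes 0 and covariates are balanced across the instrument. Even then, state that effect heterogeneity between target populations or an invalid instrument are alternative explanations.
5. If the interval includes 0, report the check as inconclusive over the range of bias that the interval allows, and do not present it as support for the absence of confounding.

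The cost is plan wording and some extra computing, with no new data. The downside is that the check may often be inconclusive.
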